10. Procedure-related complications, based on diagnosis codes documented in the EHR;
11. Adherence to recommended surveillance, for both patients and providers;
12. Effective radiation doses received.

Patient and Stakeholder Engagement: We have assembled a team of researchers, patients, clinicians and stakeholders from health systems, advocacy groups, purchasers, and professional societies to help design and execute the study, and interpret and disseminate the results. Stakeholders have contributed to the framing of the research questions and the identification and prioritization of study outcomes. The researchers on the study team have had longstanding personal and/or professional relationships with many of the patients and

stakeholders, ensuring productive collaboration within the larger group. All members of the team will have an equal voice and all contributions will be valued.

Anticipated Impact: There is concern among clinicians, purchasers, and health systems that as lung cancer screening diffuses into practice, there will be an epidemic of surveillance imaging and downstream invasive testing—testing that is inconvenient, costly and potentially harmful. By comparing accepted protocols for CT surveillance in the context of routine clinical practice, our pragmatic trial will have a large and immediate impact on clinical care. By collaborating with stakeholders from health systems, professional societies, and advocacy groups, we will disseminate our findings widely, and facilitate implementation in diverse practice settings.

Background

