Participants taking Internet surveys will provide informed consent and complete the REDCap-enabled surveys in the language of their choice, English or Spanish. Participants will be surveyed at approximately 1-2 and 13-24 months after enrollment, and at the end of surveillance.

To complement the patient perspective, we will also design a brief survey to capture provider satisfaction with the assigned protocol for surveillance and their perception about barriers to its implementation. Development of the brief physician survey will be led by [name] at UCSF, based on her ongoing qualitative pilot study of physician attitudes and beliefs about cancer screening.^{57,58} The survey will primarily focus on radiologists and ordering providers (pulmonologists and thoracic surgeons) at each study site, because they are most directly involved with lung nodule evaluation, although we will explore the possibility of surveying primary care providers. Surveys will be distributed to radiologists and ordering providers at the start of the trial and near the end of the study enrollment period (approximately mid-way through the trial).

Aim 3 Outcomes, Nodule-Related Resource Utilization and Radiation Exposure: We will compare health care resource utilization between groups by conducting searches of structured data in EHRs for relevant ICD-9 procedure codes that appear during the surveillance period (from date of the index CT scan to the date of first cancer treatment or 2 years of follow-up, whichever comes first). Most study sites use the Epic EHR, which allows for efficient searching of utilization tables; other EHR systems have similar capabilities. We will capture all relevant imaging tests (chest CT, PET,), invasive biopsy procedures (bronchoscopy, transthoracic

needle biopsy), thoracic surgical procedures, outpatient visits, emergency department visits and hospitalizations, as we have done previously for the NCI and VA-funded CanCORS study.⁵⁹ We will also record procedure-related complications by searching for diagnostic codes for pneumothorax, respiratory failure and major bleeding (relying in part on operational definitions created by the Agency for Healthcare Research & Quality Patient Safety Indicators).⁶⁰

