The primary study objectives include, among individuals with small pulmonary nodules identified either incidentally or by screening, comparing more vs. less intensive CT surveillance for the progression of cancer beyond AJCC 7th edition stage T1a disease (or T1b in the AJCC 8th edition) (Aim 1), nodule-related emotional distress (Aim 2), health care resource utilization and exposure to diagnostic radiation (Aim 3), and overall adherence with the recommended surveillance protocol (Aim 4).

The secondary objectives include comparing more vs. less intensive CT surveillance for the timeliness of lung cancer diagnosis and overall survival of patients in each study arm who prove to have a cancerous nodule (Aim 1), patient general health status and satisfaction with the evaluation process and the provider satisfaction with the surveillance protocol and the evaluation process (Aim 2), and adherence to use of low radiation-dose techniques (Aim 4). In general, we hypothesize that more intensive follow-up will result in more CT imaging (by design), greater radiation exposure, more downstream testing, greater anxiety and emotional distress, slightly shorter times to cancer diagnosis, and worse adherence to follow-up, and no effect on cancer stage distribution or overall survival.

Primary endpoints:

Aim 1: Proportion of lung cancers that are greater than 20mm

- Measured as progression beyond AJCC 7th edition T stage of T1a or, equivalently, AJCC 8th edition T stage of T1b

Aim 2: Nodule-related anxiety and emotional distress at 1-2 months, 13-24 months, and ≥25 months after nodule identification

- Measured using the IES-R and STAI-6

Aim 3:

1. Health care resource utilization within 26 months following nodule identification
 - Number of visits within 26 months of nodule identification, including the following exams (separate analyses by type of exam):
 - Chest CT scans
 - Chest x-rays
 - PET or PET/CT scans
 - Biopsies (look separately and together): Bronchoscopic biopsy, percutaneous biopsy, surgical biopsy/resection, extrapulmonary biopsy.
 - We will not include any exams after the date of cancer diagnosis, but will include biopsy that led to the cancer diagnosis
2. Serious complications within 7 days and within 30 days of a chest CT, chest x-ray, PET or PET/CT scan, or biopsy (bronchoscopic biopsy, percutaneous biopsy, surgical biopsy/resection, extrapulmonary biopsy) performed within 26 months of baseline CT:
 - Pneumothorax

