 - Pneumothorax requiring tube thoracostomy
 - Bleeding (pulmonary hemorrhage)
 - Acute respiratory failure
 - Acute renal failure
 - Allergic reaction to iodinated contrast material requiring hospitalization
 - Acute myocardial infarction
3. Cumulative radiation dose measured by DLP and effective dose

- Including radiation exposure from surveillance and diagnostic imaging following baseline CT scan through 2 years of follow-up (including 24 month exams).

Aim 4: Adherence with the recommended surveillance protocol

1. Radiologist adherence to assigned protocol
2. Physician adherence to ordering test
3. Patient adherence
 - a. Adherence to first recommended surveillance exam
 - b. Adherence to full protocol

Secondary endpoints:

Aim 1:

1. Proportion of lung cancers that are greater than 20mm, N0, MO
 - Measured as progression beyond AJCC 7th edition TNM stage of T1aN0M0 or AJCC 8th edition stage of T1bN0M)
2. Timeliness of lung cancer diagnosis
 - Measured as time from date of index CT scan to confirmed lung cancer diagnosis, defined as histologic confirmation via pathology, among individuals diagnosed with lung cancer.
3. Timeliness of lung cancer treatment
 - Measured as time from date of index CT scan to date of first treatment including surgery, radiotherapy or chemotherapy, among individuals diagnosed with lung cancer. If a patient receives no treatment, we will censor at end follow-up.
4. Overall survival of patients who prove to have a cancerous nodule,
 - Measured from date of index CT scan to death or censoring among individuals diagnosed with lung cancer.

Aim 2:

1. Patient general health status measured at 1-2 months, 13-24 months, and ≥ 25 months after nodule identification
2. Patient satisfaction with the evaluation process measured at 13-24 months and ≥ 25 months after nodule identification
3. Ordering specialist, primary care, and radiologist knowledge attitudes and beliefs about existing guidelines for pulmonary nodule evaluation measured at baseline
4. Provider satisfaction with the surveillance protocol and the evaluation process measured during the follow-up period

Aim 4: Adherence to use of low radiation-dose techniques

Hypotheses:

We specify the following hypotheses by aim:

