H3a: Among all participants with a lung nodule ≤ 15 mm, more intensive surveillance will be associated with greater nodule-related resource utilization, including more frequent use of CT scanning, PET scanning and invasive biopsy.

H3b: Among all participants with a lung nodule ≤ 15 mm, more intensive surveillance will be associated with a greater number of serious complications related to invasive procedures, including pneumothorax, pneumothorax requiring tube thoracostomy, bleeding, acute respiratory failure, acute renal failure and acute myocardial infarction.

H3c: Among all participants with a lung nodule ≤ 15 mm, more intensive surveillance will be associated with greater total exposure to diagnostic radiation than less intensive surveillance.

H4: Among all participants with a lung nodule ≤ 15 mm, more intensive surveillance will be associated with worse adherence to the surveillance protocol than less intensive surveillance, when measured at the level of the interpreting radiologist, the ordering provider and the patient.

Analysis Plan

In most cases, the unit of analysis will be the individual patient. All primary analyses will be by intention to treat, although we will also perform sensitivity analyses by surveillance imaging actually received. The intention to treat population will include all patients with qualifying nodules, even ones who do not undergo surveillance as the initial step in their evaluation (i.e., patients that proceed directly to tissue diagnosis). Sensitivity analyses will evaluate outcomes by strategy recommended and by surveillance imaging received.

Descriptive statistics will be generated for continuous variables (e.g., mean, standard deviation, median, range) and categorical variables (frequency) at baseline and follow-ups when appropriate. Bivariate analyses will include comparisons of means or medians (as appropriate) for continuously measured variables, cross tabulations of categorical variables, and Kaplan-Meier plots for time to event outcomes. Count outcomes, such as the number of procedure-related complications, will be treated as Poisson random variables. Analysis of time to

diagnosis, treatment, and survival will use Cox regression, after checking the proportionality assumption by creating log-minus-log plots.

H1a - Primary endpoint –lung cancer stage >T1a at diagnosis:

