Descriptive statistics will be generated for radiation exposure and frequency of follow-up CT scans and other nodule-related resource utilization will be obtained by site and study arm. For each type of nodule-related resource utilization, we will also create a binary variable to indicate whether a patient has any exam of that type (1 yes and 0 no) and obtain the corresponding frequency. For H3a, to examine whether among all participants with a lung nodule ≤ 15 mm, more intensive surveillance will be associated with a greater number of specific follow-up tests and types of follow-up tests (e.g., imaging, non-surgical biopsy, surgery), we will use mixed-effects Poisson regression model including random site effects to account for clustering of patients within sites. We will also model the frequency at which at least 1 specific follow-up test or type of follow-up test is performed using hierarchical logistic regression that includes random site effects. All regression models mentioned above will be fitted with and without potential confounders including age, gender, ethnicity/race, smoking, BMI, nodule size, and any facility-level factors balanced during the randomization. For H3b, to examine whether among all participants with a lung nodule ≤ 15 mm, more intensive surveillance will be associated with a greater number of serious complications related to invasive procedures, similar strategy used for H3a will be adopted. We will model the number of serious procedure-related complications using mixed-effects Poisson regression models and the frequency of patients with any serious complications using hierarchical logistic regression models. For H3c, to investigate whether all participants with a lung nodule ≤ 15 mm, more intensive surveillance will be associated with greater total exposure to diagnostic radiation than less intensive surveillance, we will use mixed effects models and log-transform the radiation exposure to make normal assumption more appropriate.

For H4, binary variables will be generated to indicate adherence to the recommended protocols measured at the level of the ordering provider and the patient. Cross tabulations of the

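### The Aim 3 complication endpoint counts events after any chest imaging, whereas H3b concerns invasive procedures; the more intensive arm therefore gets more counting time by design

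*Combined protocol and SAP*

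**What the plan says.** Under Primary endpoints, Aim 3, item 2, the plan counts "Serious complications within 7 days and within 30 days of a chest CT, chest x-ray, PET or PET/CT scan, or biopsy", for exams done within 26 months of the baseline CT. Seven events are listed. One is "Allergic reaction to iodinated contrast material requiring hospitalization".

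H3b (Hypotheses) states that "more intensive surveillance will be associated with a greater number of serious complications related to invasive procedures" and names six events after the word 'including', leaving out contrast allergy. The H3b paragraph of the Analysis Plan repeats the restriction to invasive procedures and continues: "We will model the number of serious procedure-related complications using mixed-effects Poisson regression models". A hierarchical logistic model for any event is planned alongside.

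The Aim 3 Outcomes section speaks of "procedure-related complications by searching for diagnostic codes for pneumothorax, respiratory failure and major bleeding", three events, "relying in part on operational definitions created by the Agency for Healthcare Research" and Quality; the content of those definitions is not shown.

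On exam frequency, the Objectives expect more CT in the more intensive arm by design. The section on interventions to be compared puts imaging in Group B about 30% lower.

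**The concern.** A surveillance CT or a chest x-ray is not an invasive procedure, so the listed endpoint and H3b describe different counts. Two analysts working from different sections would report different results for the same hypothesis.

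The choice matters because assignment itself changes the number of exams. If each exam opens a window, assignment sets how long a participant is watched for events. An unrelated infarction, renal failure or respiratory failure is then more likely to fall inside a window in the more intensive arm. Randomisation does not protect against this, since the number of windows arises after assignment. The planned site random effects and covariates do not remove it either. I found no rule that attributes an event to an exam, handles overlapping windows, or adjusts for their number.

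**Working it through.** **Neighbouring figures.** The plan gives no rate or power for complications, so there is no figure of its own to reproduce. Its other Aim 3 figures do reproduce. With 32,000 patients in 24 clusters (1,333 each) and ICC 0.01, the design effect is 1 + 1,332.3 × 0.01 = 14.3 and the effective size is 16,000/14.3, about 1,117 per arm. Power for 0.14 SD is 91% (stated 90%). For invasive testing, 5% v 8.4% with 15,520 per arm gives 89.5% (stated 90%).

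**Do the windows differ by arm?** Scheduled scans within 26 months from Tables C1 and C2 (incidental nodules; Group A solid rows with risk factors), A v B:
- solid ≤4 mm: 1 v 0 (one optional in B)
- solid >4 to <6 mm: 2 v 0 (one optional in B)
- solitary solid >6 to 8 mm: 3 v 2
- solid >8 mm: 3 v 2
- larger solitary non-solid: 2 v 1
- part-solid with a small solid component, and larger multiple non-solid: 2 v 2
- small multiple non-solid: 1 v 2

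So A has more windows on average, but not in every class.

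**Ratio with no true effect.** The sample-size section assumes 3.5 procedures in the more intensive arm. Applying the 30% reduction to all of them (an approximation) gives 3.5 × 0.70 = 2.45. Let w = exams × days/365 (years of window time, overlaps ignored). Let f be an assumed share of all 26-month events captured equally in both arms because the illness itself prompted an exam. With 26 months = 2.167 years:

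ratio = [2.167f + wA(1−f)] / [2.167f + wB(1−f)]

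| Window | Exams, A v B | f | Ratio |
|---|---|---|---|
| any | 3.5 v 2.45 | 0 | 1.43 |
| any | 7.5 v 6.45 (four common exams, assumed) | 0 | 1.16 |
| 30 days | 3.5 v 2.45 | 20% | 1.12 |
| 30 days | 7.5 v 6.45 | 20% | 1.08 |
| 30 days | 3.5 v 2.45 | 50% | 1.04 |
| 7 days | 3.5 v 2.45 | 20% | 1.03 |
| 7 days | 3.5 v 2.45 | 50% | 1.01 |

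For 30 days and f = 20%: wA = 0.288, wB = 0.201; (0.433 + 0.230)/(0.433 + 0.161) = 1.12.

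**Coincidental excess in A.** This is 16,000 × yearly rate × (wA − wB)(1−f). At an assumed 2–5% per year and 30 days it is 22–55 events at f = 20% and 14–35 at f = 50%.

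**False significance.** I used a two-sided 5% test of the log ratio, with variance (1/eA + 1/eB) × design effect, where eA and eB are expected events per arm. At 30 days, f = 20% and 1%, 2%, 5% events per year:
- ICC 0.01 (design effect 14.3): 5.5%, 6.0%, 7.5%
- ICC 0.001 (design effect 2.33): 8.0%, 11.1%, 20.7%

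With f = 0 the ranges widen to 6.9–15.1% and 17–62%.

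**Ratio with a true effect.** Take 5% v 8.4% invasive testing among 15,520 benign nodules per arm, plus 480 cancers per arm with one procedure each (assumed). Invasive patients number 15,520 × 0.084 + 480 = 1,784 v 15,520 × 0.05 + 480 = 1,256, a true ratio of 1.42 at equal risk per procedure. With assumed complication risks of 5–10% and the 30-day background at f = 20–50% and 2–5% per year, the observed ratio is 1.06 to 1.24. For example, 10% risk, f = 20% and 2% per year: (178 + 212)/(126 + 190) = 1.24.

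**The case against.** Imaging windows may be deliberate. Contrast allergy makes sense as an event only if imaging opens windows, and H3b omits exactly that event. H3b could therefore be an invasive subset of a broader safety endpoint, in which case its test would not carry this bias. That reading is possible, but the plan does not state it, and the analysis text gives no rule that would produce the subset.

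A reader might also infer that every mention of procedure-related complications contradicts the endpoint, including "Procedure-related complications, based on diagnosis codes documented in the EHR" in the Abstract and "Count outcomes, such as the number of procedure-related complications, will be treated as Poisson random variables" in the Analysis Plan. The documents do not support that. The Aim 3 sample-size text uses 'procedures' for non-invasive and invasive tests alike, so those mentions are compatible with imaging windows. The clear conflict is with H3b and the H3b analysis sentence that repeats it.

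Most numerical inputs are assumptions: background rates, f, the common exams, and one procedure per cancer. The 3.5 counts all procedures to the end of surveillance, and the 30% describes protocol imaging. Non-adherence (27% assumed in the more intensive group, with H4 expecting worse adherence there) would narrow the contrast. These points stand. They limit what can be said about size, not about the mismatch.

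**Conclusion.** The listed endpoint and H3b do not match. Followed as written, the endpoint gives the more intensive arm more counting time on average. With no true effect the ratio is at most about 1.43 on the inputs used, and about 1.01 to 1.16 in the scenarios with shared exams or illness-prompted capture.

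Two stronger readings are tempting and are not supported. One is that the count always favours H3b: with a real invasive excess, background events tend to dilute the ratio. The other is that the false-significance risk is known, whether reassuringly small or large. The ICC of 0.01 is given for other Aim 3 outcomes, and the result moves from 5.5–7.5% to 8–21% when the ICC is 0.001. Without a background rate or an ICC for this outcome, neither size can be settled from the documents.

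The plan should be corrected. The trial's main outcome is unaffected.

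**What to change.** For H3b, count events within 7 and 30 days after a bronchoscopic, percutaneous, surgical or extrapulmonary biopsy or a resection, performed within 26 months of the baseline CT, among all participants. Three rules should accompany this:
- Apply item 1's limit: no procedures after the date of cancer diagnosis, but include the biopsy that led to it. Otherwise complications of later therapeutic resection could enter H3b.
- Count each event once when windows overlap.
- Use one event list in Aim 3 Outcomes, the endpoint list and H3b, namely H3b's six: pneumothorax, pneumothorax needing a chest tube, bleeding, acute respiratory failure, acute renal failure and acute myocardial infarction.

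Report contrast allergy and other events in imaging windows separately as descriptive, noting that window time differs by arm by design.

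The cost is SAP wording and code; the diagnosis codes and dates are the same. H3b will have fewer events, and imaging-related harm will appear only in the descriptive report. Coincidental events nearly vanish: 1,256 invasive windows × 30/365 × 2–5% gives about 2–5 per arm. Invasive windows would still be unequal if testing differs by 3.4 points, but 15,520 × 0.034 = 528 extra windows add only about 1–2 coincidental events.

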3	All participating radiologists, ordering providers (pulmonologists, thoracic surgeons, and PCPs)	Satisfaction with surveillance protocol and notification systems	Measured with novel items, Likert-type scale during the follow-up period	Self-administered survey
		Nodule-related resource utilization and total radiation exposure	Includes all CT scans; PET scans; other imaging tests; invasive biopsy procedures (bronchoscopic and percutaneous); thoracic surgical procedures; all outpatient visits, ED visits and hospitalizations during the surveillance period	
4	All patients with nodules, random 10% sample for greater detail	Adherence with assigned surveillance protocol	EHR reviewed to determine whether surveillance imaging was completed per protocol; detailed review of radiology transcripts and orders to determine whether assigned protocol was recommended by radiologist and ordered by provider	EHR, radiology transcripts

Outcomes: The study will use readily available information from EHRs and local and statewide tumor registries to efficiently ascertain outcomes of importance to patients. We will supplement these clinical outcomes with surveys of patient-reported outcomes. The full panel of outcomes was selected based on our collective clinical expertise, and refined extensively based on iterative rounds of feedback from both clinical and non-clinical stakeholders (**Table 4**).

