that went into effect in 2013, CTDIvol and DLP must be reported in the radiology report and will be extracted from the electronic medical records. Because each site has developed their own technique for reporting the radiation dose metrics in the medical record, the technique for extracting these data will be locally determined. Effective dose, measured in milli-Sieverts (mSv), combines information about the radiation imparted to the patient, the scan location reflecting the organs irradiated, and the deleterious effect, primarily of developing cancer in the future. Effective dose increases with the dose length product and is a function of the radio-sensitivity of the tissues irradiated. Effective dose will be calculated from the DLP for each examination using existing established conversion formulas, and summed over the study period for each enrollee.

Aim 4 Outcomes, Patient and Provider Adherence: We will measure adherence to the assigned surveillance protocol at the level of the interpreting radiologist, the ordering provider, and the individual patient. First, we will measure adherence with each recommended surveillance test: was the test recommended by the radiologist, ordered by the provider, and completed by the patient? Adherence at the patient and provider levels can be extracted from structured data in the EHR. To measure adherence at the level of the interpreting radiologist, we will review a sample of radiology transcripts to determine whether the recommendation for surveillance were present and per protocol. These analyses will provide granular information about adherence on a test-by-test basis and pinpoint the level of non-adherence. In addition, we will measure overall adherence, defined as completion of all recommended tests for surveillance at the individual patient level.

Data Management

The Data Coordinating Center (DCC) at UC Davis will be the central location for data management. The DCC will collect data captured locally at each participating site. This collected

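### Aim 3 has no single cut-off: utilization stops at cancer diagnosis, but the complications endpoint does not, so it can count complications of later treatment surgery

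*Combined protocol and SAP*

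**What the plan says.** All references are to the combined protocol and SAP. Five places set the Aim 3 counting period.

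- **Primary endpoints, Aim 3, item 1 (utilization):** 26 months, with a stop at diagnosis: "We will not include any exams after the date of cancer diagnosis, but will include biopsy that led to the cancer diagnosis".
- **Primary endpoints, Aim 3, item 2 (complications):** "Serious complications within 7 days and within 30 days of a chest CT, chest x-ray, PET or PET/CT scan, or biopsy". The procedures in scope end with "surgical biopsy/resection, extrapulmonary biopsy) performed within 26 months of baseline CT". No stop at diagnosis or treatment is given.
- **Primary endpoints, Aim 3, item 3 (radiation):** "Including radiation exposure from surveillance and diagnostic imaging following baseline CT scan through 2 years of follow-up". No stop at diagnosis is given, but the type of imaging is restricted.
- **Aim 3 Outcomes, methods text:** the utilization search runs "from date of the index CT scan to the date of first cancer treatment or 2 years of follow-up, whichever comes first". The same paragraph goes on, "We will also record procedure-related complications by searching for diagnostic codes for pneumothorax, respiratory failure and major bleeding", without giving complications a window of their own. Later, effective dose is "summed over the study period for each enrollee".
- **Table 4, row for utilization and total radiation exposure:** "all outpatient visits, ED visits and hospitalizations during the surveillance period".

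The analysis text for H3b specifies mixed-effects Poisson and hierarchical logistic models and adds no cut-off. H3b concerns serious complications related to invasive procedures; H3c concerns diagnostic radiation.

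**The concern.** Items 1 and 2 stand next to each other and share nearly the same exam list and the same 26-month window, but only item 1 has the diagnosis rule. Take a patient whose needle biopsy proves cancer in month 4 and whose resection in month 5 is followed by respiratory failure. Item 1 leaves the resection out of utilization; item 2, read literally, counts its complication.

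Item 2 is a listed primary endpoint for Aim 3, and H3b uses it to ask whether more intensive surveillance causes more harm. Complications of treating proven cancer occur in both arms. They move the ratio towards 1 and make evaluation look more harmful in each arm than it is.

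**Working it through.** **1. The plan's own figure.** No power figure is given for complications or radiation. The nearest is Aim 3 procedures: 32,000 patients, 0.14 SD, ICC 0.01, two-sided alpha 0.05, 90% power. With 24 clusters, the mean cluster size is 32,000/24 = 1,333. The design effect is 1 + (1,333 − 1) × 0.01 = 14.32, and the effective n is 16,000/14.32 = 1,117 per arm. Power is 0.911, so the figure reproduces. It does not depend on the cut-off.

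**2. The rules side by side.**

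| Place | End of window | Stop for cancer |
|---|---|---|
| Item 1, utilization | 26 months | diagnosis |
| Item 2, complications | 26 months | none stated |
| Item 3, radiation | 2 years | none stated; surveillance and diagnostic imaging only |
| Methods text, utilization search | 2 years | first cancer treatment |
| Methods text, effective dose | study period | none stated |
| Table 4, utilization and radiation | surveillance period | not defined there |

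**3. Extra trigger procedures.** The plan's inputs are 15,520 benign nodules per group, 5% invasively tested, and 960 cancers.
- Benign patients tested: 2 × 15,520 × 0.05 = 1,552.
- With one work-up procedure per tested patient and per cancer (assumption): 1,552 + 960 = 2,512.
- Resection after diagnosis in 30%, 50% or 80% of cancers (assumption; not in the documents): 288, 480 or 768 more procedures.
- Increase: 288/2,512 = 11%; 480/2,512 = 19%; 768/2,512 = 31%.

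**4. Share of counted complications.** Assume 10% complications per work-up procedure and 20% per resection.
- Invasive procedures only: 57.6/(251.2 + 57.6) = 19% at 30% resected; 153.6/(251.2 + 153.6) = 38% at 80%.
- Item 2 also counts events after imaging. Take 32,000 × 3.5 = 112,000 exams (the plan's mean for the more intensive arm, applied to both arms for scale) with 0.1% to 0.5% background events (assumption), which is 112 to 560 events. The share becomes 57.6/(251.2 + 560 + 57.6) = 7% up to 153.6/(251.2 + 112 + 153.6) = 30%.

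**5. Direction.** If both arms gain the same count c and A > B, then (A + c)/(B + c) lies between A/B and 1. The rate in each arm rises; the difference A − B does not change. As an illustration, put the plan's detectable 3.4-point difference in benign testing (8.4% against 5%, a ratio of 1.68) into Group A: (776 × 1.68 + 480)/(776 + 480) = 1.42, where 776 = 15,520 × 0.05 and 480 = 960/2. With 50% to 80% resected:
- equal complication rates add 240 to 384 per arm: ratio 1.35 to 1.32;
- doubled rates for resection add 480 to 768 per arm: ratio 1.30 to 1.26.

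The 1.42 is built on a detectable difference and is not an expected effect. Imaging-triggered events are left out; including them would make the shift smaller.

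**6. Earlier diagnosis in Group A.** H1b expects it, and it would put more of Group A's treatment inside a fixed window. With 50% resected and a 5% to 20% between-arm difference in captured resections (assumption), the trigger-procedure ratio under no other difference is (1,256 + 246)/(1,256 + 234) = 1.01 to (1,256 + 264)/(1,256 + 216) = 1.03.

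**7. Radiation.** One to four post-diagnosis scans per cancer patient (assumption) add 960 to 3,840 scans, or 0.9% to 3.4% of 112,000. H3c analyses log dose. With 6 against 4 mSv, 3% cancers and 20 to 60 mSv extra in each cancer patient (all doses assumed), the log ratio is 0.97 × ln(6/4) + 0.03 × ln((6 + x)/(4 + x)). The geometric-mean ratio moves from 1.50 to 1.49 (x = 20) or 1.48 (x = 60).

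**The case against.** The best defence has three parts.

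- **The methods text may already supply a stop.** It describes complications in the same paragraph that ends the surveillance period at first cancer treatment. A reader might infer from the endpoint list that no stop exists anywhere and that treatment complications definitely will be counted. The documents do not support that; they support saying such events can be counted. But the methods text does not settle the matter. Its stop is attached to the utilization search, its 2 years conflict with item 2's 26 months, and it does not say whether a resection that is itself the first treatment falls inside.
- **Radiation is restricted by type.** A reader might infer that every restaging scan enters the dose total. Item 3, H3c and Table 4 point the other way; only the methods sentence summing dose over the study period leaves it open. The effect on log dose is small.
- **Counting everything in a fixed window is a defensible intention-to-treat choice.** Diagnosis is a post-randomisation event that may come earlier in Group A. The analysis plan for H1a itself raises overdiagnosis in the more intensive arm; complications of treating such cancers would be a real consequence of surveillance. This stands, and it is why an all-events analysis should be kept alongside. It does not explain why items 1 and 2 follow different rules.

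**Conclusion.** The concern holds for complications. Item 2 lacks the rule that item 1 states, and the methods text conflicts with item 2 without repairing it. Under assumed resection after diagnosis of 30% to 80%, trigger procedures rise by 11% to 31%. The share of counted complications is lower than an invasive-only calculation gives, and cannot be fixed from the documents. It also falls wherever the resection itself makes the diagnosis, since item 1's own wording keeps that procedure.

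A reader might also infer a substantial spurious excess in Group A from earlier diagnosis. The direction follows from H1b, but on the assumptions above it is only 1.01 to 1.03. It works against the dilution, so the net bias is not established.

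For radiation this is an ambiguity to clear up, with little effect on H3c. The Aim 1 primary result and every stated power figure are untouched. It is worth correcting because a listed primary harm endpoint is inconsistently defined and the correction is cheap.

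**What to change.** Reconcile Table 4, the Aim 3 methods text and items 1 to 3 of the endpoint list to one stated analysis cut-off.

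1. **Trigger procedures:** apply item 1's rule to item 2. Count exams and procedures up to and including the one that established the diagnosis, including a resection that did so.
2. **Events:** do not attribute to an earlier trigger an event that follows a later treatment procedure. Otherwise the 30-day look-forward from a diagnostic biopsy can bring treatment complications back in.
3. **Separate report:** tabulate post-diagnosis (treatment) complications by arm.
4. **Sensitivity analysis:** count all events in the fixed 26-month window, to cover overdiagnosis and the post-randomisation cut-off.
5. **Radiation:** state the same cut-off for DLP and effective dose.

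The cost is a few sentences and a date filter; the diagnosis date is already needed for item 1 and for time to diagnosis. The downsides are fewer counted events, a slightly wider interval, and a cut-off that may fall earlier in Group A, which item 4 addresses.
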